# **6.8.** Concomitant Therapy

- Subjects must abstain from taking prescription drugs within 14 days prior to dosing
  on Day 1 and nonprescription drugs/ over-the-counter medications (including
  vitamins and dietary or herbal supplements) within 7 days prior to dosing on Day 1
  until completion of the follow-up visit, unless, in the opinion of the Investigator and
  the Sponsor, the medication will not interfere with the study.
- Ibuprofen will be allowed during the study at recommended doses but not to exceed 2400 mg in 24 hours. Topical skin products without significant systemic absorption are permitted for use during the study at the Investigator's discretion.
- Other concomitant medication may be considered on a case-by-case basis by the Investigator in consultation with the medical monitor if required.
- Concomitant procedures are not allowed unless medically indicated.

# 6.9. Contraception Guidance

Female subjects who are documented as being of non-childbearing potential as defined in in Section 10.4 (Appendix 4) are exempt from contraception requirements.

Female subjects of childbearing potential, if heterosexually active, must use highly effective contraception as defined below, starting at least one menstrual cycle before first study drug administration and continuing for at least 3 months after the end of systemic exposure of the study drug (ie, 3 months after EOS visit).

Highly effective contraceptive methods for females are as follows:

- Combined (estrogen- and progestogen-containing) hormonal contraception associated with inhibition of ovulation as follows:
  - Oral
  - Intravaginal
  - Transdermal
- Progestogen-only hormonal contraception associated with inhibition of ovulation as follows:

- Oral
- Injectable
- Implantable
- Intrauterine device
- Intrauterine hormone-releasing system
- Bilateral tubal occlusion
- Male partner vasectomized (with documented evidence of azoospermia if possible)
- Abstinence (note: sexual abstinence is considered a highly effective method only if defined as refraining from heterosexual intercourse during the entire period of risk associated with the study treatments. The reliability of sexual abstinence needs to be evaluated in relation to the duration of the clinical trials and the preferred and usual lifestyle of the subject).

Male subjects, if heterosexually active and with a female spouse or partner of childbearing potential or a pregnant or breastfeeding spouse or partner, must agree to use barrier contraception (male condom) for the duration of the study and for at least three months after the end of systemic exposure of the study drug (ie, 3 months after EOS visit). Barrier contraception is required even with documented medical assessment of surgical success of a vasectomy. Female spouses or partners of male subjects who are of childbearing potential must use highly effective contraception as defined above, starting at least 1 menstrual cycle before (the male subject's) first study drug administration and continuing until at least three months after the end of their male partner's systemic exposure to the study drug (ie, 3 months after EOS visit). Male subjects must not donate sperm and female subjects must not donate ova for at least 3 months after the end of systemic exposure of the study drug (ie, 3 months after EOS visit).

For male subjects who have had a vasectomy (with documented evidence of azoospermia if possible) and agree to use a barrier method (male condom) for the stated time period, no additional contraceptive method is required by their female partner.

# 6.10. Intervention After the End of the Study

This is a healthy volunteer study and no follow-up intervention is planned.

# 7. DISCONTINUATION OF STUDY DRUG AND SUBJECT WITHDRAWAL

### 7.1. Discontinuation of Study Drug

Subjects who discontinue study drug, for any reason, should undergo all scheduled safety, PK and PD evaluations as specified in the Schedule of Activities (Table 1 and Table 2) in relation to the last dose they received.

If a subject withdraws consent and is unwilling to attend all scheduled procedures, then all attempts will be made to encourage them to attend for the EOS visit.

# 7.2. Subject Withdrawal from the Study

A subject may withdraw from the study at any time at his/her own request, or may be withdrawn at any time at the discretion of the Investigator for safety, behavioral, compliance, or administrative reasons.

If the subject withdraws consent for disclosure of future information, the Sponsor may retain and continue to use any data collected before such a withdrawal of consent.

Data to be collected at the time of study withdrawal and follow-up and for any further evaluations that need to be completed are specified in the Schedule of Activities (Table 1 and Table 2).

# 7.3. Lost to Follow-Up

A subject will be considered lost to follow-up if he or she repeatedly fails to return for scheduled visits and is unable to be contacted by the study site.

The following actions must be taken if a subject fails to return to the clinic for a required study visit:

- The site must attempt to contact the subject and leave a message on their primary contact number (in not answered), explaining the reason and need to attend visits. If not answered, the site will send an SMS to this number asking the volunteer to contact the site urgently.
- In parallel, the site will send an e-mail to the subject requesting the subject to attend the study visit. If no e-mail address is available, the site will send a written letter to the subject's primary address with the same information. These contact attempts must be documented in the subject's medical record.
- Should the subject continue to be unreachable, he/she will be considered to have withdrawn from the study.

### 8. STUDY ASSESSMENTS AND PROCEDURES

All screening evaluations must be completed and reviewed to confirm that potential subjects meet all eligibility criteria. The Investigator or qualified designee will maintain a screening log to record details of all subjects screened and to confirm eligibility or record reasons for screening failure, as applicable.

- Study procedures and their timing are summarized in the Schedule of Activities (Table 1 and Table 2).
- Protocol waivers or exemptions are not allowed.
- Immediate safety concerns should be discussed with the Sponsor's medical monitor immediately upon occurrence or awareness to determine if the subject should continue or discontinue study drug.
- Adherence to the study design requirements, including those specified in the Schedule of Activities, is essential and required for study conduct.
- All screening evaluations must be completed and reviewed to confirm that potential subjects meet all eligibility criteria. The Investigator will maintain a screening log to record details of all subjects screened and to confirm eligibility or record reasons for screening failure, as applicable.
- Procedures conducted as part of the subject's routine clinical management (eg, blood count) and obtained before signing of the ICF may be utilized for screening or baseline purposes provided the procedures met the protocol-specified criteria and were performed within the time frame defined in the Schedule of Activities.

# 8.1. Efficacy Assessments

No efficacy assessments will be obtained during this study.

# 8.2. Safety Assessments

Planned time points for all safety assessments are presented in the Schedule of Activities (Table 1 and Table 2).

# 8.2.1. Physical Examination

A full physical examination will be performed at screening and at Period 1 and Period 2 admission (Day -1). A symptom-driven physical examination will be performed at the EOS visit and may be performed at other times, at the Principal Investigator's discretion.

Each examination will include the following assessments: general appearance; skin; head, ears, eyes, nose, and throat; neck; lymph nodes; chest; heart; abdominal cavity; limbs; central nervous system; and musculoskeletal system.

Height (screening only) and weight will also be measured and recorded at screening and EOS visit. Body mass index will be calculated and recorded at screening.

### 8.2.2. Vital Signs

Vital sign measurements will be taken after the subject has been resting in the supine position for at least 5 minutes and will include temperature (°C; tympanic), respiratory rate (RR), supine blood pressure, and pulse rate (PR). Orthostatic (standing) blood pressure will only be measured at screening. The timing of vital sign measurements is described in the Schedule of Activities (Table 1 and Table 2). Out of range blood pressure or PR measurements will be repeated at the Investigator's discretion. Confirmed, clinically significant vital sign measurements will be recorded as AEs.

### 8.2.3. Electrocardiograms

#### 8.2.3.1. Recording of 12-lead ECGs

A triplicate 12-lead ECG will be obtained using a GE Marquette MAC1200® / MAC1200ST® recorder connected via a fixed network connection to the MUSE® Cardiology Information System (MUSE) after the subject has been resting for at least 10 minutes. ECGs will be conducted before PK/PD/biomarker blood sampling if these 2 events occur at the same time. The timing of ECGs is described in the Schedule of Activities (Table 1 and Table 2).

ECGs recorded during screening will be stored electronically on the MUSE information system. Only ECG recorded electronically will be valid ECG for any purpose other than safety assessment. ECG printouts may be filed in the subject's case report form (CRF) for medical safety reviews.

Each ECG recorder will be set up to the required technical specifications and containing the information required to identify the records. Each ECG recording will be clearly identified (Subject ID, visit date, and the actual times of ECG recordings).

12-lead ECG recordings will be made after the subjects have been resting in a supine position for at least 10 minutes. The subjects will avoid postural changes during the ECG recordings and clinical staff will ensure that subjects are awake during the ECG recording.

At each time point, the ECG will be recorded in triplicate, to reduce variance and improve the precision of measurement. The triplicates will be performed at approximately 1-minute intervals. Each ECG recording (trace) will last 10 seconds. Repeat ECG will be performed until at least three 10-second ECG records per scheduled time-point meet the quality criteria set out in the Study Operations Manual and the applicable Standard Operating Procedure to enable reading and analyzing at least 5 complexes per derivation.

#### 8.2.3.2. Safety Review of 12-lead ECGs

All recorded ECG will be reviewed by the Investigator, or qualified designee, and the review findings will be documented in the CRF. If a subject shows an abnormal ECG, additional safety recordings (including the use of 5- or 12-lead Holter equipment) may be made and the abnormality be followed to resolution, if required.

### 8.2.4. Clinical Safety Laboratory Assessments

All protocol-required laboratory assessments, as defined in Section 10.2 (Appendix 2), must be conducted in accordance with the Schedule of Activities (Table 1 and Table 2) and the laboratory

manual. Clinical and laboratory assessments will be performed by a local laboratory to assess safety of ALXN1840.

- The Investigator must review the laboratory report, document this review, and record all clinically relevant changes occurring during the study in the AE section of the CRF. The laboratory reports must be filed with the source documents.
- All laboratory tests with values considered clinically significantly abnormal during
  participation in the study will be repeated until the values return to normal or baseline
  or are no longer considered clinically significant by the Investigator or medical
  monitor.
  - If such values do not return to normal/baseline within a period of time judged reasonable by the Investigator, the etiology should be identified and the Sponsor's medical monitor should be notified.
  - If laboratory values from non-protocol-specified laboratory assessments performed at the institution's local laboratory require a change in subject management or are considered clinically significant by the Investigator (eg, SAE or AE or dose modification), then the results must be recorded in the CRF.
- The maximum amount of blood to be collected from each subject over the duration of the study, including any extra assessments that may be required, will not exceed 500 mL. Repeat or unscheduled samples may be obtained for safety and/or eligibility reasons or if there are any technical issues with the samples. Please refer to the laboratory manual for specific details regarding plasma sampling volumes.

### 8.2.5. Drug and Alcohol Screen

A urine sample for drug screen will be analyzed for the substances listed in Section 10.2 (Appendix 2). Timing of urine drug and alcohol breath tests is specified in the Schedule of Activities (Table 1 and Table 2).

### 8.2.6. Pregnancy Testing

Pregnancy testing will be performed in serum for all female subjects at the time points specified in the Schedule of Activities (Table 1 and Table 2).

### **8.3.** Adverse Events and Serious Adverse Events

The definitions of an AE or SAE and specific reporting requirements are located in Section 10.3 (Appendix 3). Adverse events will be reported to the Investigator or qualified designee by the subject (or, when appropriate, by a caregiver, surrogate, or the subject's legally authorized representative).

The Investigator and any qualified designees are responsible for detecting, documenting, and recording events that meet the definition of an AE or SAE and remain responsible for following up AEs that are serious, considered to be related to the study drug or study procedures, or that caused the subject to discontinue the study drug (see Section 7).

### 8.3.1. Time Period and Frequency for Collecting AE and SAE Information

All AEs and SAEs will be collected from the ICF until the EOS visit.

Medical occurrences that begin before the first dose of study drug and after obtaining informed consent will be recorded on the CRF, and will be considered as medical history.

All SAEs will be recorded and reported to the Sponsor or designee within 24 hours, as indicated in Section 10.3 (Appendix 3). The Investigator will submit updated SAE data to the Sponsor within 24 hours of the data being available.

Investigators are not obligated to actively seek AEs or SAEs after the conclusion of study participation (ie, after the EOS visit).

The method of recording, evaluating, and assessing causality of AEs and SAEs and the procedures for completing and transmitting SAE reports to the Sponsor are provided in Section 10.3 (Appendix 3).

### **8.3.2.** Method of Detecting AEs and SAEs

Care will be taken not to introduce bias when detecting AEs and/or SAEs. Open-ended and non-leading verbal questioning of the subject is the preferred method to inquire about AE occurrences.

### 8.3.3. Follow-up of AEs and SAEs

After the initial AE/SAE report, the Investigator is required to proactively follow each subject at subsequent visits/contacts. All SAEs will be followed until resolution, stabilization, the event is otherwise explained, or the subject is lost to follow-up (as defined in Section 10.3 [Appendix 3]). Further information on follow-up procedures is provided in Section 10.3 (Appendix 3).

### 8.3.4. Regulatory Reporting Requirements for SAEs

- Prompt notification by the investigator to the Sponsor of a SAE is essential so that legal obligations and ethical responsibilities towards the safety of subjects and the safety of a study intervention under clinical investigation are met.
- The Sponsor has a legal responsibility to notify both the local regulatory authority and other regulatory agencies about the safety of a study intervention under clinical investigation. The Sponsor will comply with country-specific regulatory requirements relating to safety reporting to the regulatory authority, IRB/IEC, and Investigators.
- Investigator safety reports must be prepared for suspected unexpected serious adverse reactions (SUSAR) according to local regulatory requirements and the Sponsor's policy and forwarded to investigators as necessary.
- An Investigator who receives a safety report describing a SAE or other specific safety information (eg, summary or listing of SAEs) from the Sponsor will review and then file it along with the IB and will notify the IRB/IEC, if appropriate according to local requirements.

## 8.3.5. Pregnancy

• Incidence of all pregnancies in female subjects and if indicated female sexual partners of male subjects will be collected after the administration of study drug and for at least 3 months after the EOS visit thereafter.

- Complications of abnormal pregnancy outcomes (eg, spontaneous abortion, fetal death, stillbirth, congenital anomalies, and ectopic pregnancy) are AEs and may meet the criteria for SAEs (Section 10.3 [Appendix 3]).
- If a pregnancy is reported, the Investigator should inform the Sponsor or designee within 24 hours of learning of the pregnancy. Specific pregnancy information to be collected is outlined in Section 10.4 (Appendix 4).

## 8.4. Safety Review Committee

An ad-hoc Safety Review Committee must convene within 24 hours in the case of a possible treatment-emergent serious adverse event (TESAE) considered to be related to study drug or the withdrawal of subjects due to TEAEs considered to be related to study drug in order to determine whether any stopping rules apply and the impact on study continuation (see Section 6.6 and Section 6.7).

There is an option to have additional ad-hoc Safety Review Committee meetings to discuss urgent issues should the need arise. The membership roster and requirements for documenting meeting discussions and outcome will be outlined in the Safety Review Committee charter. Further internal or external experts may be consulted by the Safety Review Committee as necessary.

#### 8.5. Treatment of Overdose

No cases of overdose have been reported during ALXN1840 clinical studies. Study drug will be administered and monitored by site personnel.

## 8.6. Pharmacokinetics

Whole blood samples will be collected for the measurement of plasma total Mo (PK) over time as specified in the Schedule of Activities (Table 1 and Table 2). Additional samples may be collected during the study if warranted and agreed upon between the Investigator and the Sponsor. The actual date and time (24-hour clock time) of each sample will be recorded. Other PK concentration measurements including, but not limited to, that of plasma ultrafiltrate (PUF) Mo may be conducted.

Additional samples may be collected during the study if warranted and agreed upon between the Investigator and Alexion. Details including further handling and processing instructions and sampling-time windows will be provided in the study laboratory manual.

## 8.7. Pharmacodynamics

After study drug administration, whole blood samples will be collected for the measurement of plasma total Cu and non-ceruloplasmin-bound copper (NCC) over time as specified in the Schedule of Activities (Table 1 and Table 2). Calculations will also be performed for NCC and

corrected NCC (NCCcorrected), the latter of which is non-Cp-bound and non-Mo-albumin-bound Cu. Detailed calculation formulae will be provided in the statistical analysis plan (SAP). The actual date and time (24-hour clock time) of each sample will be recorded.

Additional samples may be collected during the study if warranted and agreed upon between the Investigator and the Sponsor. Details including further handling and processing instructions and sampling-time windows will be provided in the study laboratory manual.

## 8.8. Genetics

Genetics will not be evaluated in this study.

## 8.9. Biomarkers

After study drug administration, whole blood samples will be collected for the measurement of plasma Cp and ceruloplasmin-bound copper (CpC) as biomarkers as specified in the Schedule of Activities (Table 1 and Table 2). Other biomarker concentration measurements, including but not limited to, that of PUF Cu may be conducted.

The actual date and time (24-hour clock time) of each sample will be recorded. Additional samples may be collected during the study if warranted and agreed upon between the Investigator and the Sponsor. Details including further handling and processing instructions and sampling-time windows will be provided in the study laboratory manual.

## 9. STATISTICAL CONSIDERATIONS

## 9.1. Statistical Hypotheses

Not applicable.

## 9.2. Sample Size Determination

The study sample size is not based on hypothesis testing with statistical considerations. A sample size of 20 subjects (10 subjects in each cohort) has been selected based on practicality and convention for this type of study. Considering potential for subject drop-out of the study, a total of 24 subjects will be enrolled with 12 Japanese and 12 non-Japanese. The between-subject coefficient of variation (CV) in a previous bioavailability study using 2 × 30 mg EC tablets (Study WTX101-102) was 35%, which can be used to approximate the standard deviation (SD). Two cohorts of 10 subjects produce a two-sided 90% confidence interval with a distance from the difference in means to the limits that is equal to 0.271. For example, if the difference of means is zero and the ratio of means is 1, this level of precision corresponds to an interval from 0.76 to 1.31 on the ratio scale.

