enteric-coated (EC) tablet fasted compared to the UC + PPI fasted. Similar trends were observed with respect to maximum observed concentration ( $C_{max}$ ), AUC to the last measurable concentration (AUC[0-t]), and AUC with the last concentration extrapolated based on the elimination rate constant ( $\lambda z$ ) (AUC[inf]). Nevertheless, examination of the individual subject data indicated that while a similar pattern was observed with some of the individual subjects, the majority of the subjects had a total Mo concentration-time profile that was comparable for the EC tablet and UC + PPI when both were administered under fasted conditions. However, administration of the EC tablet fed resulted in a 60% to 75% decrease in absorption which was consistent among the majority of subjects. The mean  $t_{1/2}$  was essentially the same for all 3 treatments, with an overall mean of ~48 hours or 2 days (Table 4).

Table 4: Total Mo PK Parameters from Study WTX101-102

D	Treatment			
Parameter a	EC Tablet Fasted	EC Tablet Fed	UC + PPI Fasted	
T lag (h)	2.00 (4)	3.00 (6)	b	
C max (ng/mL)	$376 \pm 98.0 (18)$	$187 \pm 118  (17)$	442 ± 69.6 (18)	
t max (h)	4.54 (18) [3.00 – 9.53]	4.55 (17) [3.52 – 9.51]	4.50 (18) [2.99 – 10.0]	
AUC (o-t) (h*ng/mL)	$16,026 \pm 5,635 $ (18)	5,740 ± 4,681 (17)	19,809 ± 3,509 (18)	
AUC ∞ (h*ng/mL)	$17,258 \pm 5,955 $ (18)	$6,973 \pm 5,065 $ (15)	21,047 ± 4,022 (17)	
$\lambda_{z}$ (1/h)	$0.0149 \pm 0.0023$ (18)	$0.0258 \pm 0.0303 \ (15)$	$0.0145 \pm 0.0014$ (17)	
t 1/2 (h)	51.0 ± 8,87 (18)	$43.5 \pm 20.9 (15)$	48.2 ± 4.86 (17)	
CL/F (L/h)	$0.92 \pm 0.51 (18)$	$6.34 \pm 11.9 (15)$	$0.66 \pm 0.13 (17)$	
Vz/F (L)	$66.6 \pm 34.0 \ (18)$	$175 \pm 98.1 (15)$	45.2 ± 8.31 (17)	

<sup>a Arithmetic mean  $\pm$  standard deviation (N) except for  $t_{max}$  for which the median (N) [Range] is reported.

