#### *4.12.3 Pharmacokinetic Analysis for Ethnic Difference*

The PK parameters for total Mo ( $C_{\text{max}}$ ,  $\text{AUC}_t$ , and  $\text{AUC}_{\infty}$ ) will be evaluated for Japanese and non-Japanese cohorts, using an analysis of variance (ANOVA) statistical model [1,2] with cohort and period as the fixed effects, and subject as a random effect, using the natural logarithms of the data. The within-subject CV for the  $C_{\text{max}}$ ,  $\text{AUC}_t$ , and  $\text{AUC}_{\infty}$  will be estimated using the mean squared error from the ANOVA. The mean between-group differences and their 90% and 95% CIs are back-transformed to the linear scale and represent estimates of ratios of geometric means.

In addition, the Japanese versus non-Japanese cohorts will be evaluated using descriptive statistics: for each cohort, the geometric means and the associated 95% confidence intervals of  $C_{\text{max}_n}$ ,  $\text{AUC}_{t_n}$ , and  $\text{AUC}_{\infty_n}$  will be reported at each dose.

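### Is the stated 90% interval of 0.76 to 1.31 too narrow because a 35% CV was entered as the log-scale SD?

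*Protocol*

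**What the plan says.** Protocol 9.2 and SAP 3.3 carry the same text. The sample size of 10 per cohort "has been selected based on practicality and convention for this type of study", and Protocol 9.1 lists no statistical hypothesis. The text then takes a between-subject CV of 35% from the EC tablets in Study WTX101-102, without naming a PK parameter, as a value "which can be used to approximate the standard deviation (SD"). The stated half-width of the two-sided 90% interval is 0.271. For a true ratio of 1, given as an example, "this level of precision corresponds to an interval from 0.76 to 1.31 on the ratio scale".

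The cohort comparison itself is set out in SAP 4.12.3. Cmax, AUCt and AUC∞ enter an ANOVA "with cohort and period as the fixed effects, and subject as a random effect, using the natural logarithms of the data". The section continues: "The mean between-group differences and their 90% and 95% CIs are back-transformed to the linear scale", which gives ratios of geometric means.

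**The concern.** Three things look wrong. First, one precision figure is given for three primary parameters, and the text does not say which of them the 35% describes. Second, the analysis is on the log scale, so the input should be a log-scale SD, and a CV equals that only approximately. Third, Table 4 (Protocol 2.2) shows a much larger CV for CL/F than for AUC∞ in the same arm. If CL/F is a constant divided by AUC∞, log-normal data would give both the same CV apart from sampling variation. The gap suggests that the log-scale spread of AUC∞ exceeds 0.35.

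The interval is the only quantitative statement of how finely the study can compare the cohorts. If it is too narrow, a reader would expect better resolution than the study delivers.

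**Working it through.** **1. The plan's own figure.** Half-width = t(0.95, 18 df) × SD × √(2/10) = 1.734 × 0.35 × 0.4472 = 0.271, and exp(∓0.271) = 0.762 to 1.312. The stated figures are reproduced, with 0.35 entered directly as the log SD. For 10 per cohort the multiplier is 0.7755.

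**2. Where 35% comes from.** Table 4, EC tablet fasted, n = 18, arithmetic mean ± SD:

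- AUC(0-t): 5,635/16,026 = 35.2%
- AUC∞: 5,955/17,258 = 34.5%
- Cmax: 98.0/376 = 26.1%
- CL/F: 0.51/0.92 = 55.4%

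The 35% matches AUC, not Cmax. That it is an arithmetic CV is an inference from this match; Protocol 9.2 does not say so.

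**3. The usual conversion.** For log-normal data, log SD = √ln(1 + CV²) = √ln(1 + 0.35²) = 0.340. The half-width is 0.7755 × 0.340 = 0.264, or 0.768 to 1.302. On this check alone the stated interval is slightly too wide.

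**4. Adding the CL/F row.** SAP 4.12.2 defines CL/F as dose/AUC∞; assume WTX101-102 did the same up to a constant factor. The factor is needed because 60 mg/17,258 h·ng/mL is about 3.5 L/h, against 0.92 in Table 4. A constant does not affect the CV. I then take all sets of 18 positive values with mean 17,258, SD 5,955 and a reciprocal CV between 0.505/0.925 = 0.546 and 0.515/0.915 = 0.563 (the rounding limits of CL/F). The log SD in such sets runs from 0.362 to 0.463, so 0.35 is not attainable.

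Both ends are artificial. The lower is 4,825, sixteen values of 16,719, and 38,320. The upper is four values of 7,049, one of 12,293 and thirteen of 20,781. Without the lowest value their log SDs are 0.201 and 0.429. Protocol 2.2 reports that "the majority of the subjects had a total Mo concentration-time profile that was comparable for the EC tablet and UC + PPI" under fasting, so a few low-exposure subjects may explain the excess, but the documents do not show where in the range the truth lies.

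**5. Single dose, 10 per cohort.**

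| Log SD | Half-width | Interval at ratio 1 |
|---|---|---|
| 0.35 (plan) | 0.271 | 0.762-1.312 |
| 0.362 | 0.281 | 0.755-1.324 |
| 0.41 (mid-range) | 0.318 | 0.728-1.374 |
| 0.463 | 0.359 | 0.698-1.432 |

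For Cmax, if log-normal, log SD = √ln(1 + 0.261²) = 0.256, half-width 0.199, interval 0.82-1.22. Table 4 has no reciprocal row to test that assumption. For AUC(0-t) there is no such row either.

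**6. The planned ANOVA.** Each subject contributes both doses. With complete data and the same log SD at each dose, the variance of a subject's mean is SD² − s²/2, where s² = ln(1 + CVw²) and CVw is the within-subject CV. The documents give no CVw, so a range is assumed. At log SD 0.41 with 10 per cohort:

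- CVw 10%: √(0.1681 − 0.0050) × 0.7755 = 0.313, interval 0.731-1.368
- CVw 30%: √(0.1681 − 0.0431) × 0.7755 = 0.274, interval 0.760-1.315

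The stated half-width of 0.271 is reached at a CVw of 13%, 31% or 45% for log SD 0.362, 0.41 or 0.463. With all 12 enrolled per cohort it is already met at 0.362, and is reached at 19% and 37% for the other two.

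**7. Uncertainty of any planning SD.** With 18 subjects and normal theory (an assumption), 95% limits for an SD are about 0.75 to 1.50 times the estimate. Around 0.463 the lower limit is 0.75 × 0.463 = 0.347, so even the upper bound is compatible with a true value of 0.35.

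**The case for a change.** The case for a correction is that the direction is not a matter of judgement: given the CL/F relation, no data set consistent with Table 4 has a log SD for AUC∞ as low as 0.35. The routine conversion in step 3 even points the wrong way. The plan prints the half-width to three decimals, the sponsor has the individual data of a completed study, and a reader will apply one interval to all three primary parameters.

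The narrow point stands: for AUC∞ at one dose, 0.35 is below what the 18 past subjects showed, by an amount between negligible and moderate. It also stands that the parameter is unnamed. It does not extend further. Nothing is established for AUCt. For Cmax the stated interval is probably too wide, although Protocol 2.2 notes "Similar trends were observed with respect to maximum observed concentration" when describing the lower exposure with the EC tablet, so low values may be shared. Nor is the single-dose 90% interval a planned output: the cohort ratio by dose (Frel, SAP 4.12.2) gets a 95% interval, and the 90% interval comes from the model that pools both periods. For that model no error has been shown. Finally, the bound describes one earlier sample; it does not make 0.35 a wrong planning value for a new one.

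**Conclusion.** The arithmetic in Protocol 9.2 is right and its input is a declared approximation. For AUC∞ at a single dose with 10 completers per cohort, the stated 0.76-1.31 is too narrow by an amount ranging from one unit in the second decimal of one limit (0.755-1.324) to a moderate difference (0.698-1.432). This assumes that CL/F was proportional to 1/AUC∞ in WTX101-102. For the two-period ANOVA the stated half-width may be about right, depending on a within-subject CV that the documents do not give.

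No change follows because the figure decides nothing. The number of subjects rests on practicality and convention, there is no hypothesis or margin, and the reported intervals will use the variance observed in this trial. A better value cannot be derived from the documents; it would need the individual WTX101-102 data and would leave design, sample size, analysis and conclusions as they are. The missing parameter name is a gap that a reader can fill from Table 4, where 35% is recognisably the AUC figure.
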